## ***Template Instructions***

### ***Sections that do not apply:***

- *In several sections, the addition of checkboxes for **Not Applicable** have been added to the template as responses.*
  - *If an N/A checkbox is present, select the appropriate justification from the list.*
  - *If an N/A checkbox is not present, or if none of the existing checkboxes apply to your study, you must write in your own justification.*
- *In addition:*
  - *For research where the only study procedures are records/chart review: Sections 19, 20, 22, 23, 24, 25, 31, and 32 do not apply.*
  - *For exempt research: Sections 31 and 32 do not apply.*

### ***Studies with multiple participant groups:***

- *If this study involves multiple participant groups (e.g. parents and children), provide information in applicable sections for each participant group. Clearly label responses when they differ. For example:*

#### **Response Example**

Intervention Group:

Control Group:

### ***Formatting:***

- *Do not remove template instructions or section headings when they do not apply to your study.*

*If you are pasting information from other documents using the “Merge Formatting” Paste option will maintain the formatting of the response boxes.*

### ***Amendments:***

- *When making modifications or revisions to this and other documents, use the **Track Changes** function in Microsoft Word.*
- *Update the version date or number **on Page 3.***

**PROTOCOL TITLE:**

*Include the full protocol title.*

Response:

Improving adherence to a diabetic diet with a grocery shopping intervention

**VERSION NUMBER/DATE:**

*Include the version number and date of this protocol.*

Response 11 – 05/04/2020 (final version)

All changes from the original protocol and Clinicaltrials.gov registration were minimal and are detailed herein.

**REVISION HISTORY**

Revision #	Version Date	Summary of Changes	Consent Change?
1	3/28/19	Changes made in response to clarifications requested: unbolded payment on recruitment postcard, removed date from HIPAA form and added detail on how this information is confirmed, unchecked pregnant women in section 6.3, checked box in 7.1, provided further detail on recruitment/social media, indicated waiver of consent requested, with justification, clarified voluntary nature of participating in consent document	Yes
2	4/11/19	Changes made in response to clarifications requested: recommended statement added to consent, formatting of protocol template was checked/updated as requested, NA was added to 6.1 and 6.2, additional details on social media use were added, the term de-identified was changed to coded throughout, requested	Yes

		modifications were made to the HIPAA form, and recruitment postcard was checked/edited as requested.	
3	6/28/19	We have made the following changes: receipts will be collected for the household; modifications to inclusion criteria – participant needs to do 75% of the grocery shopping for household and needs to complete at least 75% of grocery shopping at Wegman's/Tops; changed number of recipes cards provided (3 per week). We also made a few minor additions/changes to questionnaire/interview: asking how long they were in the store shopping; whether they use insulin; how they liked the recipes from the study; whether they follow a special diet; and a question about their liking of several possible recipes. We also modified our food frequency questionnaire (to ask about the past month rather than year given the time frame of our study) and added a receipt form to allow participants to clarify what the items on their receipts are. All of these changes are included in the modification in tracked changes (in this protocol/the relevant attachments).	
4	7/24/19	We made minor changes after internal feasibility testing of the protocol. These include: removing part of our baseline questionnaire (corresponding changes are tracked in the protocol and study script/questionnaire attachments) and minor changes to the script/receipt form to streamline procedures, now asking questions about who the purchased food items are for on the receipt forms rather than the phone interview. We also specify our stratification factors in the protocol. All of these changes are included in the modification in tracked changes (in this protocol/the relevant attachments)	
5	9/16/19	We have changed the consent procedure to include written consent consistent with SOP and full HIPAA authorization after challenges acquiring participant medical information from clinicians. All of these changes are included in this modification in tracked changes (in this protocol/the relevant attachments).	

6	9/30/2019	
We have made the following changes: adding pre-diabetes/type II diabetes eligibility criteria to the front of the recruitment materials (flyer, postcard, and Facebook advertisement) to make this criteria more visible for interested individuals; modifying our eligibility script to align with the SOP consent/HIPAA form; expanding recruitment as described herein (collaborating with partners within our department, at Independent Health Foundation, I2B2 and ResearchMatch; adding an additional mode of communication with physicians' offices (fax via eFax.com, to maintain confidentiality because our lab does not have a private fax machine); adding an option for participants to receive study documents via postal mail if that is their preference. We have also made minor changes to eligibility criteria where participants must shop at Tops/Wegmans at least 50% of the time (instead of 75% of the time). A number of interested participants were deemed ineligible solely because of this criterion, leading the study team to review the inclusion criteria and their purposes. While it is important that participants shop at these stores regularly, the selection of the specific cutoff was somewhat arbitrary, and upon revisiting, the study team felt that a cutoff of 50% or more would still capture the majority of the household's shopping and would facilitate greater participation without affecting the rigor of the study. An additional option was added to the screener document to encompass this change in eligibility criteria. We have also added a question to the screener document asking participants if they have recently participated in (or are currently in) any other research studies and to explain the nature of each study. Additionally, we have changed our enrollment procedures to allow participants to self-report and start the study before confirming their diabetes status with a physician. This decision was made because of feasibility concerns; a number of eligible participants have not been able to enroll in the study as a direct result of
	
---	-----------	---	--

		extended delays in communication between study staff and physician's offices; this change will allow for faster turnover and study progress, while still allowing for the confirmation of diabetes status later in the study. All of these changes are included in the modification in tracked changes (in this protocol/the relevant attachments)	
7	11/5/2019	We have made the following changes: Addition of a joint recruitment postcard and flyer to be used by our study as well as two other studies recruiting similar populations within the Division of Behavioral Medicine (STUDY00002659 and STUDY00003608) so that we may efficiently direct participants to the study that might suit them. We have also created a shared online questionnaire that will be used solely to direct participants to the IRB-approved online screening questionnaire for the aforementioned studies. No personally identifiable information will be collected on this survey; it is completely anonymous. All of these changes are included in the modification in tracked changes (in this protocol/the relevant attachments)	
8	12/10/2019	We have made the following changes: Given the remote nature of this study (all participant contact takes place via phone, email, or postal mail), we have elected to expand our recruitment efforts past the Buffalo area to include the greater Northeastern US, where Tops and Wegmans stores are located. For this reason, we have added an additional question to the screener asking potential participants to input their home zip code; this will help us determine whether the participant is within the specified distance to Tops and/or Wegmans stores, and if they are eligible to receive Instacart delivery services in their area. We have also edited the protocol to specify that recruitment will extend beyond the Buffalo area to include the Northeastern US. All of these changes are included in the modification in tracked changes (in this protocol/the relevant attachments)	

9	02/20/2020	We have made the following changes: We plan to collaborate with the UB contracted media-buying agency Fahlgren Mortine (FM) for study recruitment. FM has created a customized media plan specific to our study objectives, and we have developed a new recruitment material for digital display advertising. This has been adapted from previously approved material to better suit a digital display platform, and a user-friendly vanity link has been created to direct interested individuals to our screening survey (which remains unchanged). All of these changes are included in the modification in tracked changes (in this protocol/the relevant attachments)	
10	03/12/2020	We have made the following changes to the protocol in response to the COVID-19 pandemic: We will allow study team members to work remotely on UBs secure VPN as a preventative measure to limit person contact. The study team has been instructed to maintain confidentiality as in the lab setting and to perform study tasks in a private space in accordance with laboratory emergency procedures.	
11	05/04/2020	We have made the following changes: We have modified our definition of “at risk for diabetes” after learning that few individuals have a formal prediabetes diagnosis. We are still interested in recruiting individuals with type 2 diabetes and type 2 diabetes risk, but now, instead of defining this as type 2 diabetes or prediabetes diagnosis, we are defining it as type 2 diabetes diagnosis OR at risk for type 2 diabetes based on a diagnosis of prediabetes or meeting criteria for increased risk of developing type 2 diabetes based on the American Diabetes Association Type 2 Diabetes Risk Test (described further herein). This affects the questions we ask on our screening questionnaire and the wording of some of our materials; uploaded attachments have been included and described in the modification submission. We have also extended our study timeline and prepared additional language and measures in response	Yes

		to the COVID19 pandemic; these include tempering the language about in-person grocery shopping for the control group, so that it doesn't feel like it is required if not preferred in the context of COVID-19, and adding changes in daily life, perceived stress and loneliness measures within our baseline and post surveys. Additionally, we added newspapers and periodicals, and the Clinical and Translational Sciences Institute (CTSI) Community Liaison and Buffalo Research Registry (BRR) to our recruitment methods to aid in the recruitment of participants from the greater Buffalo community. We also changed the mention of added sugar to sugar and/or added sugar throughout the protocol, as we do plan to examine at least one of these, but realized in beginning our data entry processes that examination of added sugar in particular may be difficult with the current nutritional software/analysis plan.	
--	--	---	--

## FUNDING:

*Indicate any funding for this proposal. This should match the Funding Sources page in Click IRB.*

Response:

This research is being funded by the Clinical and Translational Science Institute.

## GRANT APPLICABILITY:

*Indicate whether this protocol is funded by a grant (e.g. NIH, foundation grant). For a grant with multiple aims, indicate which aims are covered by this research proposal.*

*NOTE: This question does not apply to studies funded by a sponsor contract.*

 *Include a copy of the grant proposal with your submission.*

Response:

Response: A grant proposal to fund this work was submitted to the CTSI in December 2018 and has been funded with a start date of 4/1/2019 (pending IRB approval). The grant is attached.

### 1.0 Study Summary

Study Title	Improving adherence to a diabetic diet with a grocery shopping intervention
Study Design	
This study has an experimental design. Participants will be randomly assigned to 1 of 2 interventions or a control group in which they will shop in-person as usual. Stratification factors will be sex and diabetes status: diabetic vs. at risk for type 2 diabetes, defined as a diagnosis of prediabetes or meeting criteria for increased risk of developing type 2 diabetes in accordance with the American Diabetes Association Type 2 Diabetes Risk Test. In all groups, recipe cards that follow the evidence-based DASH diet will be provided; recipes correspond to dietary recommendations for patients with type 2 diabetes or at increased risk of developing type 2 diabetes. The Online intervention will utilize online grocery shopping (shopping at a local grocery store via Instacart) to promote healthier purchasing, removing visceral factors that can lead to impulse purchases in stores. The Defaults intervention will augment this intervention, showing participants a default cart when they log into their accounts. They will be told that their cart has been filled with items that conform to a diet for diabetes prevention, management, and overall health and can be used to make the recipes from the provided recipe cards, and that they may modify it as they like.
 
At baseline, all participants will complete a survey online or via phone and then will grocery shop in-person as usual. Participants will then be randomized and receive further instructions. For the next 3 weeks, they will receive recipe cards and shop in accordance with their assigned study group. The following week (post), they will shop using their preferred mode (in-person or online) and complete a survey again. Household receipt data will be collected throughout

	the study. The baseline period will also serve as a run-in period, and participants who do not comply with study guidelines for baseline procedures (including guidelines for receipt submission) will not be randomized for further participation. Primary analyses will examine intervention effects on grocery purchases, with additional analyses on spending and dietary intake. The study is designed, so that all participant interactions will occur remotely: online, via phone, or through paper mail (study materials may be sent via paper mail if it is the participants preference, and Clincards for participant payment will initially be sent via mail as is standard, using participant addresses as already collected on the consent form).
Primary Objective	The goal of this study is to test novel approaches informed by behavioral economics to promote healthier grocery shopping among adults with type 2 diabetes or at an increased risk of developing type 2 diabetes.
Secondary Objective(s)	The specific aims are: (1) to test effects of Online and Defaults grocery shopping interventions on the grocery purchases of adults with type 2 diabetes or at risk of developing type 2 diabetes and (2) to explore effects of the Online and Defaults interventions on participants' spending during grocery shopping. We will also explore effects on dietary intake.
Research Intervention(s)/ Investigational Agent(s)	There will be two interventions in this study. The first intervention is the Online intervention, which will utilize online grocery shopping (shopping at a local grocery store via Instacart) to promote healthier purchasing, removing visceral factors that can lead to impulse purchases in stores. The second intervention, the Defaults intervention, will augment the Online intervention, showing participants a default cart when they log into their accounts. They will be told that their cart has been filled with items that conform to a diet appropriate for diabetes prevention, management, and overall health and can be used to make the recipes from the provided recipe cards, and that they may modify their carts as they like.
IND/IDE #	
Study Population	Adults diagnosed with type 2 diabetes or at increased risk of developing type 2 diabetes, defined as a diagnosis of prediabetes or meeting criteria for increased risk of developing type 2 diabetes in accordance with the American Diabetes Association Type 2 Diabetes Risk Test
Sample Size	Up to 100

Study Duration for individual participants	An individual subject's participation in the study will take place over about 6 weeks.
Study Specific Abbreviations/ Definitions	

## 2.0 Objectives\*

*2.1 Describe the purpose, specific aims, or objectives of this research.*

Response:

The goal of this study is to test novel approaches informed by behavioral economics to promote healthier grocery shopping among adults diagnosed with type 2 diabetes or at increased risk of developing type 2 diabetes, defined as a diagnosis of prediabetes or meeting criteria for increased risk of developing type 2 diabetes as determined by the American Diabetes Association Type 2 Diabetes Risk Test. The specific aims are: (1) to test effects of *Online* and *Defaults* grocery shopping interventions on participants' grocery purchases and (2) to explore effects of the *Online* and *Defaults* interventions on participants' spending during grocery shopping.

*2.2 State the hypotheses to be tested, if applicable.*

*NOTE: A hypothesis is a specific, testable prediction about what you expect to happen in your study that corresponds with your above listed objectives.*

Response:

It is hypothesized that (1a) purchases made by adults in the Defaults group will be lower in calories, carbohydrates, and sugar (total sugar and/or added sugar) and higher in nutritional quality (DASH diet score) at post-test versus other study groups, (1b) adults in the Defaults group will show the greatest increases in nutritional quality versus other study groups, (1c) the Online group will have intermediary results between Defaults and Controls, and (2) there will be no difference in total dollars depicted on receipts across study groups during the intervention period (i.e., the costs of online shopping will be offset by effects of the Online and Default interventions).

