## **19.0 Data Management and Analysis\***

*19.1 Describe the data analysis plan, including any statistical procedures. This section applies to both quantitative and qualitative analysis.*

Response:

Linear mixed models will be used to test effects of the interventions on total calories, carbohydrates, sugar (total sugar and/or added sugar), and nutritional quality of grocery purchases, with study group, time, and their interaction as factors. Primary comparisons will be between-groups comparisons of these variables at post-test. We will also examine whether these variables differ overall by study group and whether changes in these variables differ by study group. We will conduct each analysis once for the total cart and then again examining these variables relative to household size and for items that the respondent indicated they would be consuming. We will conduct parallel analyses with total dollars spent each week and with DASH diet scores as outcomes to examine effects on spending and intake. We will also explore whether effects differ for participants with prediabetes vs. diabetes and whether results change when adjusting for food purchases beyond the target stores. Finally, we will test for relationships between purchases (calories, carbohydrates, and sugar (total sugar and/or added sugar)) and intake (DASH diet scores). We will also explore whether results differ when considering shopping trips completed by the participant only (vs. all trips for the household).

*19.2 If applicable, provide a power analysis.*

*NOTE: This may not apply to certain types of studies, including chart/records reviews, survey studies, or observational studies. This question is asked to elicit whether the investigator has an adequate sample size to achieve the study objectives and justify a conclusion.*

Response:

To estimate the sample size needed for this study, effect sizes from the most similar existing study were used: a proof-of-principle study examining the effects of defaults, incentives, and education strategies on healthfulness of grocery purchases among undergraduate students (Coffino & Hormes, 2018, Obesity). Based on the observed differences in calories purchased at post-test between defaults and education control groups (Cohen's  $d=0.96$ ), 15 participants would be needed for the primary comparison in the present study, with  $\alpha=.05$  and  $\text{power}=.80$ . We repeated this analysis using the difference between controls and

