the prior study's intermediary group (incentives; Cohen's  $d=0.44$ ) to conduct a more conservative sample size calculation, given our interest in detecting effects on purchasing between our intermediary group (*Online*) and the other groups. This calculation yielded a sample size of 54. We increased this to account for participants lost during the run-in period (i.e. failure to confirm diabetes diagnosis, failure to complete baseline procedures) as well as participants lost due to attrition, with a plan to enroll up to 100 participants.

*19.3 Describe any procedures that will be used for quality control of collected data.*

Response:

Some data will be entered directly by participants (online questionnaires). All other study data will be entered by trained staff: study staff will enter participant responses into online forms while phone screening/phone interviews are completed. Study staff will also enter information from receipts into NutritionistPro (e.g., nutrition information) and Microsoft Excel (e.g., dollars spent) for analysis of study aims. Entered data will be double entered and/or checked for quality control.

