## **27.0 Compensation for Participation**

27.1 *Describe the amount and timing of any compensation to subjects, including monetary, course credit, or gift card compensation.*

Response:

All participants will receive up to \$75 for their participation in the study, with \$20 provided after completing baseline measures (\$20), \$10 after each intervention measure, and another \$25 provided after post-test. Participants will be paid as they complete study tasks using Clincard. Clincards will be provided after all screening procedures are completed, and eligibility (and interest in participating) has been determined. Payments during intervention weeks will also include reimbursements for typical costs of online shopping in Online and Defaults groups, given that these participants typically shop in-person but are being asked to shop online as part of the study. The typical cost of online shopping was estimated by applying Instacart service fees (5% of purchase) and data on average mark-ups on Wegmans items purchased via Instacart (~15% of purchase) to weekly grocery shopping amounts estimated using the USDA's official food plans (moderate-cost plan for a given family size:

<https://www.cnpp.usda.gov/sites/default/files/CostofFoodMar2019.pdf>). We also added the estimated cost of delivery (\$5.99) to the estimates. The payment to subsidize costs of online shopping will be calculated in this manner for each participant based on their family size. For example, for a 19-50-year-old single female participant, the USDA's moderate cost plan estimates \$59.60 in weekly food expenditures. Calculating the costs of online shopping indicated above (service fees, item mark-ups, and delivery) at this budget, we will provide an additional \$53.73 to this participant over the course of the study (\$17.91 per intervention week). For a family of two adults, this estimate changes to \$103.47 or \$34.49 per intervention week. As with other study payments, these payments will be provided to participants via Clincard provided they complete the study activities of the week.

☐ **N/A:** This study is not enrolling subjects, or is limited to records review procedures only. This section does not apply.

- ☐ **N/A:** There is no compensation for participation. This section does not apply.

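### Hypothesis 2 predicts equal spending and reads it as online costs being offset, but the plan has only tests of difference for spending, with no margin, confidence-interval rule or named intervention-period contrast

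*Combined protocol and SAP*

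**What the plan says.** Section 2.2 lists hypothesis 2 among those to be tested: "there will be no difference in total dollars depicted on receipts across study groups during the intervention period". It glosses this to mean that "the costs of online shopping will be offset by effects of the Online and Default interventions". The matching aim in section 2.1 is worded more softly: "to explore effects of the *Online* and *Defaults* interventions on participants' spending during grocery shopping".

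Section 19.1 specifies linear mixed models for the purchase outcomes, "with study group, time, and their interaction as factors". It makes the between-group comparison at post-test primary, and adds overall group differences and group differences in change. Spending gets one clause: "We will conduct parallel analyses with total dollars spent each week". No equivalence or non-inferiority margin, interval rule or power for spending appears anywhere. The sample size in section 19.2 rests on calories purchased.

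Under section 12.1, the three weeks after randomization are the only ones in which the shopping mode is assigned. At post-test everyone shops by whichever method they prefer, without default carts or recipe cards. Section 27.1 adds: "Payments during intervention weeks will also include reimbursements for typical costs of online shopping in Online and Defaults groups".

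**The concern.** Hypothesis 2 is a claim of equivalence. A test of difference can count against it but cannot support it, because failing to reject is compatible both with equal spending and with a real excess that the data are too noisy to show. With only such a test planned, the noisier the spending data and the smaller the sample, the better hypothesis 2 appears to fare.

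The time window is also loose. Hypothesis 2 concerns the intervention weeks, but the comparison named as primary falls in a week when nobody is assigned to shop online, so it cannot show whether the cost of assigned online shopping was offset.

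At stake is a statement that online grocery shopping adds no net cost. Section 4.1 contemplates recommending it to patients in clinical care, so readers would use that statement.

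**Working it through.** **1. Cost at stake (section 27.1).** The protocol applies a 5% service fee, about 15% item mark-up and $5.99 delivery.
- Single adult: 0.20 × 59.60 + 5.99 = $17.91 per week, and 3 × 17.91 = $53.73. Both match the protocol. 17.91 / 59.60 = 30%.
- Two adults: the stated $34.49 implies a weekly budget of (34.49 − 5.99) / 0.20 = $142.50. 34.49 / 142.50 = 24%.

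**2. Group size.** Section 19.2 says "This calculation yielded a sample size of 54". Read per group this would need 3 × 54 = 162 participants, above the cap of 100, so I read it as a total. It reproduces as a total of 54 for a three-group, two-time-point group-by-time interaction (d = 0.44, f = 0.22, assumed correlation 0.5). That gives 54 / 3 = 18 per arm. The cap of 100 gives at most about 33 per arm with no losses. Equal allocation is assumed.

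**3. Which planned contrast fits hypothesis 2.**
- Post-test comparison: outside the intervention period.
- Overall group effect: if it averages all five weeks equally, and a difference exists only in the three intervention weeks, it shows 3/5 of that difference. A 30% excess appears as 18%, and a 24% excess as about 14%.
- Group differences in change: closest to what is needed, but the time points are not named.

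**4. Chance of missing a real excess.** To be fair to the plan, I use a contrast that exploits baseline: the mean of the three intervention weeks minus the baseline week. The documents give neither an SD nor a correlation, so the following are assumptions: between-week correlation r = 0.7, weekly SD equal to CV × mean, and two-sided α = 0.05 (sidedness is not stated).
- Variance factor = (1 + 2r)/3 + 1 − 2r = 0.8 + 1 − 1.4 = 0.4, so SD = CV × √0.4.
- Noncentrality = (excess / SD) × √(n/2), with 2n − 2 degrees of freedom.
- Example: CV 50% gives SD = 31.6%. A 20% excess gives d = 0.63. At n = 18 the noncentrality is 1.90 and the miss rate is 55%. At n = 33 it is 2.57 and 28%.

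Miss rates for a true 20% overspend (for a single adult, about one third of the modelled 30% cost has been offset):

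| CV | 18 per arm | 33 per arm |
|---|---|---|
| 30% | 13% | 1% |
| 50% | 55% | 28% |
| 70% | 74% | 56% |

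At CV 50%, r = 0.5 (factor 0.667) gives 70% and 50%, and r = 0.8 (factor 0.267) gives 38% and 13%. If none of the single-adult cost were offset (30% excess, CV 50%, r = 0.7), the miss rates are 21% and 3%.

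**5. What an equivalence rule would deliver.** With baseline as a covariate the variance factor is (1 + 2r)/3 − r² = 0.8 − 0.49 = 0.31. At CV 50%, SD = 50% × √0.31 = 27.8%. The 90% CI half-width, t(0.95) × SD × √(2/n), is about ±16% at 18 per arm and ±11% at 33. With an illustrative ±15% margin and no true difference, equivalence would be concluded about 4% and 40% of the time.

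**The case against.** The strongest reply is that spending is secondary by design. Aim 2 is worded as exploratory, the Study Summary lists spending under additional analyses, section 3.0 confines the primary analyses to nutritional outcomes, and section 8.4 describes the study as a pilot. That stands, and it limits the severity.

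A reader might infer that the investigators will treat a non-significant result as proof of no difference. The documents do not say so. They give no rule for reading a spending result. What can be said is that nothing in the plan is capable of supporting hypothesis 2.

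A reader might also infer that the intervention weeks are left out of the spending analysis. They are not: dollars are collected weekly, and the overall and change analyses use those weeks. The gap is that no contrast is named for hypothesis 2.

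Finally, comparing raw three-week means, with CV 50% and r = 0.7, would miss a 30% overspend 50% of the time at 18 per arm and 23% at 33. Those figures overstate the weakness, because the planned model includes the baseline week. The change contrast gives 21% and 3%, and baseline as a covariate gives 12% and 1%. A total failure to offset would therefore often be detected. Partial offset is where the plan is weak.

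**Conclusion.** The concern holds as a mismatch between hypothesis and analysis, and that part rests on the text alone. Hypothesis 2 asserts equality during the intervention period, while the plan offers only tests of difference, with no margin, no interval rule and a primary comparison in the wrong week.

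The size of the problem depends on an unknown SD. It is small if weekly spending varies by 30% and about 33 per arm are analysed. It is substantial at a CV of 50% or more, or at 18 per arm. Mixed household sizes would raise the SD unless spending is scaled. Baseline adjustment reduces the miss rates but does not mend the logic.

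A reader might infer that the trial's main result is in doubt. It is not, because only the spending conclusion is affected. The plan should be corrected on this point, but the point is not critical.

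**What to change.** In section 19.1, name the contrast for hypothesis 2: mean weekly dollars over the three intervention weeks, adjusted for baseline spending, for Online vs Control and Defaults vs Control. Report each estimate with its confidence interval. Then choose one of two courses before the data are analysed:

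- Pre-specify and justify a margin smaller than the modelled online cost (24% to 30% in the protocol's examples). Conclude no difference, or offset, only if the 90% CI lies wholly within it. Otherwise report the result as inconclusive.
- Keep the aim exploratory, report estimates and intervals only, and remove the offset conclusion from section 2.2.

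Under either course, state beside the result that only the Online and Defaults groups were reimbursed for online costs, so their spending may not reflect that of households paying those costs themselves. Also state which fees the receipt totals contain, since the documents do not say. A subtotal before fees and delivery would still include the item mark-up.

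The change costs some wording and one interval per comparison, with no new data. The drawback is that the first course will probably be inconclusive at this sample size, as step 5 of the working shows. For an exploratory aim, the second course is adequate.
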